13.2.4. Sample Size Calculations

Because the objective of the Provider Training Study (Phase II) is to pilot test the newly developed provider training intervention, we do not conduct sample size calculations for this phase of the study, with the sample of 6-8 providers chosen based on what is feasible to accomplish in a pilot. Instead, sample size justification is provided below for the Patient Training Study. We will calculate pre-post effect sizes to inform a larger R01 trial that is expected to follow from this study.

13.3. Outcomes and Statistical Analyses for Patient Training Study (Phase III)

13.3.1. Primary Outcomes

- (1) Patients' **self-efficacy** and **outcome expectancies** for communicating about sexual health with their provider, and
- (2) (A) **The proportion of visits in which the patient asks at least one question pertaining to sexual health**, and (B) **the proportion of clinic visits in which the patient raises the topic of sexual health**, both at post-training clinic visit

13.3.2. Secondary Outcomes

- (1) Feasibility and acceptability, as measured through recruitment and retention rates, and by acceptable responses on the Program Evaluation
- (2) Sexual function, as measured through the PROMIS SexFS Brief Profile (Female) score
- (3) Sexual activity, as measured through a single item on the PROMIS SexFS Brief Profile (Female)
- (4) Patients' self-efficacy (measured via the PEPPi-5 and 6 additional self-efficacy items) and outcome expectancies for communicating about treatment side effects in general and menopausal health with their provider,
- (5) Patients' self-reports of barriers to communicating about sexual health
- (6) Patient self-reports of psychological health (Hospital Anxiety and Depression scores)
- (7) Patient self-reports of QOL (FACT-B total score)

An exploratory outcome may also be the number of questions a patient asks overall per visit. Additional outcomes are shown in the Patient Training Study Patient Self-Report Measures Table. Data will be obtained on these other measures

to generate hypotheses which can be tested in future studies and will be analyzed according to standard procedures, similar to those described for the main outcomes as below.

13.3.3. Analyses

Primary Analyses

Prior to conducting primary analyses, we will generate summaries of all variables. Demographic and medical variables will be summarized using descriptive statistics (means, medians, standard deviations, frequencies, proportion missing, etc.). We will assess the distribution of all continuous measures (particularly outcome measures), and if appropriate, normalizing transformations will be applied.

Generalized linear mixed models with appropriate link and variance functions will test for the effects of patient training on beliefs (self-efficacy, outcome expectancies) over time. We will include intervention arm, indicators for timepoint (T2 and T3 vs T2), and an interaction between time and treatment arm. If the interaction between time and treatment arm is significantly different from zero, we will conclude that the intervention influenced beliefs at follow-up (T2/T3). If linear regression models are appropriate, stratification factors (disease stage, education) will be included as covariates to reduce variance. We will use nested random effects (times within patients, patients within providers) to account for multiple sources of correlation.

Prior to conducting quantitative analyses, the audio recorded clinic visits will be coded, using a similar strategy as described for the Provider Training Study (Phase II), which centers on the newly developed sexuality dialogue codebook, but can also include other communication behaviors or topics that emerge as important through the coding analyses. To test the hypothesis that patient communication behaviors differ for those in the Skills-based vs. Control conditions, we will use Fisher's exact tests. If a patient asks 1 or more questions during the visit, they will be coded as "yes" for outcome 2A and "no" otherwise. If a patient brings up the topic of sexual health they will be coded as "yes" for outcome 2B. If no one brings up the topic of sexual health, they will be coded as "no". If the provider brings up sexual health, these visits will be excluded from analysis of outcome 2B, as it is impossible to know if the patient may have brought up sexual health if the doctor had not done so. In preliminary data from phase II, these communication behaviors were so rare that Fisher's exact tests will be primarily used. If possible, we will also conduct logistic regression analyses accounting for within-provider correlation using random effects (estimated via generalized linear mixed models, similar to the models described above).

In supplementary analyses, we may examine patient factors that may moderate effects on patient outcomes (e.g., age, partnered status, metastatic disease) by including the moderator, study arm, and study arm by moderator interaction terms in generalized linear mixed models. We may also conduct secondary regression analyses to verify the conclusions of primary models, to assess the sensitivity of inferences to the assumptions of the mixed effects models. For example, we may use Generalized Estimating Equations as confirmatory models, or use logistic or ordinal logistic regressions if the semi-continuous outcome measures cannot be transformed so that the assumptions of the linear regression model are met.

Secondary Analyses

Feasibility and acceptability of the intervention will be analyzed using descriptive analyses. Recruitment rate is operationalized as the proportion of screened and eligible candidates who choose to enroll on the study. Based on our other sexuality trials, a recruitment rate of $\geq 30\%$ will be considered acceptable. Retention is operationalized separately as the proportion of enrolled study subjects who end up completing all study surveys. A retention rate $\geq 70\%$ will be considered adequate. Acceptability is measured through scores on responses to items in the Program Evaluation form. If $\geq 75\%$ of participants indicate "Satisfied" or "Very satisfied" on item 15 of this scale (the overall satisfaction item) at post-treatment, that will indicate adequate overall acceptability of the program. Other items on this scale will also be

analyzed descriptively and the information will supplement about the other data points on the acceptability of the program.

We will also determine whether the skills-based program effected pre-post differences (T3 – T1) for the secondary outcomes of: sexual function, sexual activity (active vs. not active), patients' communication self-efficacy and outcome expectancies, patients' self-reports of barriers to communicating about sexual health, and patient self-reports of psychological health (Hospital Anxiety and Depression scores) and patient self-reports of QOL (FACT-B total score). Similar to the analyses conducted for primary outcome 1, we will use generalized linear mixed models or hierarchical logistic regression models (if outcome is dichotomous), to determine the effect of the intervention arm on these measures. T2-T1 differences will also be analyzed for the beliefs measures.

Exploratory Analyses

If possible, exploratory analyses will be conducted, where we will look at the number of questions patients ask per visit. We will use Poisson or Negative Binomial models for these count outcomes, and will consider zero-inflated models if appropriate. Additional analyses of other exploratory measures will be conducted using generalized linear mixed models, similar to those performed for Primary aim 1. Also, we will explore potential mediation effects, specifically, whether self-efficacy mediates the intervention effect on belief outcomes. We do not anticipate sufficient power for a formal mediation analysis, but we will gather preliminary estimates of effect sizes which may be used to design future studies.

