Study Design: First, we will identify barriers and preferences for patient-provider communication about sexual concerns and practical and preferred methods for administering the provider and patient training programs. Using qualitative interviews and focus groups with both providers and patients, we will design provider and patient training programs and refine them through expert team review and mock trainings and tailor an intimacy enhancement intervention for breast cancer survivors. Second, we will test the feasibility and acceptability of the training program in a new group of 6-8 providers, and examine change in providers' beliefs up to 6-months post-training. We expect that the frequency and quality of provider communication behaviors relating to sexuality will increase following training through coding pre- and post-training audio recorded clinic dialogue and/or through patient self-reports of communication that occurred during the clinic visits. Third, we will randomize 144 breast cancer patients with sexual concerns to a brief Skills-Based Training plus menopausal and sexual health resources or a Control condition (menopausal and sexual health resources only) prior to a routine clinic visit with a trained provider. We expect that the Skills-based training program will be feasible and acceptable and that patients will exhibit greater increases in pre- to post-training beliefs at 2-month follow-up compared with patients in the Informational Control condition. Through coding audio recorded clinic visits immediately following training, we expect that patients receiving the Skills-based training will ask more questions and express more concerns pertaining to sexuality than control patients. In additional analyses, we will examine the impact of training on psychological health, sexual function and activity, and QOL at 2-month follow-up. In a separate forthcoming study, we will pilot test the newly tailored Intimacy Enhancement intervention which will follow from the information gathered in the exploratory aim.

Significance: The lack of discussion about sexual concerns relative to the severity and importance of these concerns to women with breast cancer make this issue a major priority. The programs we develop will address an important, undertreated area of concern for breast cancer patients. Addressing breast cancer patients' sexual concerns can enhance patient-centered care and improve patients' intimate relationships and QOL.

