4.3.3. Patient Training Study Design (Phase III)

Immediately after consent, patients will be administered a baseline self-report survey. The table on the following page shows the anticipated schedule of self-report measures to be completed by patients participating in the Patient Training Study (Phase III) as well as the number of items and estimated length of time needed to complete the survey at both time points. Assessments will primarily be conducted using RedCap forms, which are HIPAA compliant and convenient for participants, particularly for baseline (T1) and 2-month follow-up data (T3), whereas post-intervention (T2) data will generally be collected primarily in-person in clinic immediately following the clinic visit which was audio recorded. However, survey data may be administered using paper-based forms in the case that patients are unable or unwilling to complete online surveys and can be collected either through the mail or in person; telephone collection may also be used if needed to facilitate efficient and timely gathering of follow-up data. Medical data will be collected from medical records and include: stage of disease, dates of diagnosis, surgeries, and treatments, and current and past breast cancer treatments.

We will use block randomization to randomize patients 1:1 to either condition with stratification by (a) metastatic disease (Stage IV) vs. non-metastatic disease (anything other than Stage IV) and (b) education (less than or equal to 12 years of education, i.e., a high school diploma) vs. any more than a high school education (equivalent to more than 12 years of education) to assign 64 patients to the Skills-based training plus menopausal and sexual health resources and 64 patients to the Control condition (menopausal and sexual health resources only).

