The patient training intervention will consist of multiple aspects such as PowerPoint slides with voiceover and audio or video clips, along with a workbook. The materials will be sent to participants using a RedCap link, after consent, completion of baseline surveys, and randomization. Patients will be able to complete the intervention either at home using their own computer or other device, or in-person in a private location at Fox Chase, either in advance of their clinic visit or the day of their clinic visit. This flexibility will allow patients without computer access to participate, while still maintaining a consistent time frame in which the assessments and intervention will be delivered.

Patient Training Study (Phase III) Patient Self-Report Measures					
Measure	# Items	Minutes to Complete	Baseline	Post-Training	2-Month Follow-up
Demographics	7	5	X	-	-
Patient-Provider Communication Self-Efficacy (PEPPI-5)	5	3	X	X	X
Beliefs (Self-efficacy/Outcome expectations) ^{67,75}	18	5	X	X	X
Barriers to discussing sexual health	13	4	X	-	X
Self-Report of Communication During Patient Visit	20	10	-	X	-
Hospital Anxiety and Depression Scale (HADS)	27	10	X	-	X
Dyadic Adjustment (DAS-4) ⁷⁶	4	2	X	-	X
Quality of Life (FACT-B Brief) ⁷⁷	23	10	X	-	X
HRQOL Items	10	4	-	X	-
PROMIS SexFS Brief Profile Version 2 (Female) ⁷⁸	14	5	X	-	X
Information/Help-Seeking ⁷⁹	3	2	X	-	X
Therapeutic Aids ⁸⁰	3	3	X	-	X
Satisfaction with Interaction with Provider ⁸¹	4	2	-	X	-
Program Evaluation (Skills-Based Training patients only)	20	10	-	X	-
Resources Evaluation	6	3	-	X	-
Totals					
- Baseline (T1)	117	49			
- Post-Training (T2)	77	37			
- 2-Month Follow-up (T3)	126	44			

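### The primary belief model takes T2 as reference where T1 is meant, does not name the contrast that decides the 2-month hypothesis, and leaves the power available from the T1 score unused

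*Combined protocol and SAP*

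**What the plan says.** Section 13.3.3 (Primary Analyses) tests the effect of training on self-efficacy and outcome expectancies with generalized linear mixed models containing arm, "indicators for timepoint (T2 and T3 vs T2), and an interaction between time and treatment arm". If that interaction differs significantly from zero, "we will conclude that the intervention influenced beliefs at follow-up (T2/T3"). The correlation structure is described as follows: "We will use nested random effects (times within patients, patients within providers"). Disease stage and education are the only covariates listed.

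Four other places bear on this:

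- Section 4.3.3 fixes the labels: "particularly for baseline (T1) and 2-month follow-up data (T3), whereas post-intervention (T2) data". T1 is therefore baseline, T2 is right after the recorded visit, and T3 is 2 months. The measures table there shows beliefs collected at all three. The training materials go out "after consent, completion of baseline surveys, and randomization", so the T1 score precedes allocation.
- Section 1.0 states the belief hypothesis: "patients will exhibit greater increases in pre- to post-training beliefs at 2-month follow-up compared with patients in the Informational Control condition".
- Section 13.3.1 gives the communication outcomes a time ("both at post-training clinic visit") but gives the belief outcomes none.
- Under Secondary Analyses, section 13.3.3 uses T3 − T1 for the secondary outcomes, with models like the primary one, and adds: "T2-T1 differences will also be analyzed for the beliefs measures".

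Section 13.3.4 bases the sample size on beliefs: 64 per arm, 80% power, standardised effect 0.5, two-sided 5%. It also mentions an assumed effect of 0.60.

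**The concern.** There are three linked points about the model for the outcome that sets the sample size.

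1. The time coding sets T2 against itself and leaves T1 no place. This is plainly a slip for T1. It needs correcting because the secondary analyses are modelled on the same text.
2. With T1 restored there are two interaction terms, arm × T2 and arm × T3. The plan speaks of one interaction and a conclusion about T2/T3, which most naturally means a joint test with 2 degrees of freedom. That test is valid, but it cannot tell an effect seen only right after the visit from one still present at 2 months, and section 1.0 asks about 2 months. If the contrast is not named in advance, the choice stays open until the data are seen.
3. An arm main effect lets the two arms have different baseline means (a free baseline). This is unbiased, but randomisation makes the true baseline means equal. Using that fact, or the T1 score as covariate, gives a more precise estimate from data already collected.

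**Working it through.** **Inputs.** From section 13.3.4: 64 per arm, effect 0.5 (or 0.60), two-sided 5%. Assumed: equal correlation ρ between any two time points (a patient random intercept gives this), complete data, an identity link, no provider clustering, and effects in SDs of a single measurement. The documents give no ρ, so it is varied.

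**Step 1: the plan's figure.** For a two-group comparison at one time point, the noncentrality is δ√(n/2) = 0.5 × √32 = 2.83. The noncentral t gives 80.1% power at 64 per arm, so the stated 80% reproduces. At 0.60 the power is 92.0%. This calculation contains no time-by-arm interaction.

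**Step 2: the reference level.** Taken literally, only T3 against T2 is left. An effect of 0.5 at both times then gives an interaction of 0.5 − 0.5 = 0, and power equals the 5% test level. This cannot be what is meant. T1 is the reference from here on.

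**Step 3: which test decides.** With a free baseline, the joint test has noncentrality n(d₂² − d₂d₃ + d₃²)/[3(1 − ρ)], where d₂ and d₃ are the effects at T2 and T3. For (0.5, 0.5) and for (0.5, 0) the bracket in the numerator is 0.25. Both cases therefore give 16/[3(1 − ρ)] = 7.62, 10.67 and 17.78 at ρ = 0.3, 0.5 and 0.7. Power is 68.4/83.2/97.0% by the F distribution, or 69.5/84.1/97.3% by chi-square. The joint test is thus equally likely to succeed whether the effect lasts or vanishes.

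Simulation, 20,000 trials per cell, free baseline, both tests at 5% (ρ = 0.3/0.5/0.7):

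| Effect at T2, T3 | Joint test significant | Arm × T3 significant | The two disagree |
|---|---|---|---|
| 0.5, 0.5 (sustained) | 68.8/83.0/96.9% | 66.4/79.9/95.2% | 16.7/11.9/3.8% |
| 0.5, 0.25 (halved) | 55.6/70.7/90.9% | 22.2/28.9/44.3% | 37.8/44.4/47.5% |
| 0.5, 0 (gone) | 68.8/83.1/96.9% | 5.2/4.9/5.2% | 64.0/78.4/91.8% |

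**Step 4: use of T1.** The variance of the arm × T3 estimate is (2/n) × 2(1 − ρ) with a free baseline and (2/n)(1 − ρ²) with a common baseline mean. The ratio is (1 − ρ²)/[2(1 − ρ)] = (1 + ρ)/2. A generalised least squares calculation with all three time points agrees.

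| ρ | 0.3 | 0.4 | 0.5 | 0.7 |
|---|---|---|---|---|
| Variance ratio | 0.65 | 0.70 | 0.75 | 0.85 |
| Power at 0.5, free | 66.0% | 72.7% | 80.1% | 95.2% |
| Power at 0.5, common | 83.7% | 86.5% | 90.0% | 97.6% |
| Power at 0.60, free | 81.2% | 86.8% | 92.0% | 99.2% |
| Power at 0.60, common | 94.2% | 95.7% | 97.3% | 99.7% |
| Per arm for 80% at 0.5, free / common | 89 / 59 | 77 / 54 | 64 / 49 | 39 / 34 |
| Per arm for 80% at 0.60, free / common | 63 / 41 | 54 / 38 | 45 / 34 | 28 / 24 |

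With a free baseline, arm × T3 reaches 80% at 64 per arm if ρ is at least about 0.50 (effect 0.5) or about 0.28 (effect 0.60). It also does so if the effect was defined in SDs of the change score.

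**The case against.** - **Most of this is minor or optional.** The reference level is a typing slip that the documents themselves resolve, and the free-baseline model is valid. The gain from T1 depends on an unknown ρ: at 0.7 it is under 3 points for an effect of 0.5 and under 1 point for 0.60. All of this is true, and none of it is presented here as a bias or as a proven power shortfall.
- **The joint test is inferred.** The plan never names it, and its conclusion about T2/T3 is correct even after an effect at T2 alone. That stands. The large disagreement in the last row of the simulation follows from asking two different questions. But an unnamed test is the problem itself, and a correct statement about T2/T3 still leaves the 2-month hypothesis undecided.
- **T3 may not be the intended time.** In Hypothesis II (section 2.3.2) the 2-month phrase could attach only to sexual function and other health outcomes, and Primary Objective II gives no time for beliefs. This is fair, and it is why a stated joint test is an acceptable answer. Section 1.0 does tie beliefs to 2 months.
- **The secondary analyses already name contrasts.** They do, but as secondary analyses. The self-efficacy and expectancy measures in the T3 − T1 list may be the general and menopausal ones in section 13.3.2, not the primary ones.
- **The power levels are idealised.** Nested random effects do not by themselves fix equal correlations, and 64 is a count of recordings. At the 70% retention the plan accepts, 0.70 × 72 ≈ 50 per arm. Power for 0.5 at ρ = 0.5 is then 69.7% free and 81.6% common. The levels fall; the gain remains.

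**Conclusion.** The concern holds on all three parts and should be fixed. The reference level is misstated, and the evident intention is T1. The deciding contrast for the primary belief outcomes is not given. On the most natural reading, the test could be significant in about 69 to 97% of trials for an effect that has vanished by 2 months, against about 5% for arm × T3. Using T1 cuts the variance of the 2-month contrast to (1 + ρ)/2 of its planned value, a gain at every correlation between 0 and 1. At 0.5 SD and 64 per arm that is about 18 points of power at ρ = 0.3, 10 at 0.5 and 2 at 0.7.

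These sizes rest on the assumptions listed with the inputs, above all on a ρ that the documents do not supply. The planned model is unbiased, and the 80% claim is unsupported for this contrast rather than shown to be wrong.

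**What to change.** In section 13.3.3:

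- Define the time indicators as T2 and T3 against T1, each interacting with arm.
- Name arm × T3 as the deciding test for each belief score, in line with section 1.0, with arm × T2 secondary. If a joint test is preferred, say so and state that it supports no claim about 2 months.
- Choose in advance one way of using T1: a common baseline mean for both arms in the three-time-point model, or the T1 score as covariate in a linear model of T2 and T3. The two are close with complete data and an identity link, but not in general.
- Treat the continuous T3 − T1 secondary outcomes likewise. For sexual activity, T1 status can enter the logistic model as a covariate; the text should then note that the odds ratio is conditional on it.

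In section 13.3.4, state the contrast, the effect scale and the within-patient correlation behind the 80%.

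Naming the contrast settles the time point only. How the two belief scores are combined is a separate matter. The cost is a few sentences of analysis-plan wording, with no extra patients, data or procedures.

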13.3.4. Sample Size Calculations

The sample size calculations are based on the primary belief outcomes. Based on prior literature,⁹⁰ we assume a standard effect size of .60 on the outcome of patient beliefs. We therefore aim to accrue up to 144 patients (72 per arm) in order to collect an estimated 128 audio recordings (64 per arm) to have 80% power to detect a standard effect of 0.5, with 5% two-sided type-I error.

Other primary outcomes include A) the proportion of visits where the patient asks a question, and B) the proportion of visits where the patient brings up sexual health. Based on preliminary data, we expect these proportions to be low in the control arm (15% and 22%, respectively). We also anticipate that 70% of visits will be informative for outcome B (only visits where the physician does NOT bring up sexual health to be included). Therefore, with sample size of 128 audio recordings, we will have 80% power with 5% 2-sided type-I error to detect rates of 38% for outcome A in the intervention arm versus 15% in the control arm (calculations using Fisher's exact test). For outcome B, assuming 45 informative visits per arm, we will have sufficient power to detect rates of 52% in the intervention arm versus 22% in the control arm.

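### Section 13.3.3 leaves the within-patient covariance of the belief scores at nested random effects; read as random intercepts, this can miscalibrate the T3-T1 and T2-T1 contrasts, though a joint interaction test is only mildly affected

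*Combined protocol and SAP*

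**What the plan says.** The belief model in Section 13.3.3 (Primary Analyses) is a generalized linear mixed model with arm, time-point indicators and their interaction. On correlation it says: "We will use nested random effects (times within patients, patients within providers) to account for multiple sources of correlation". It names no random slope, residual covariance structure or robust standard error for this model. The success rule is that the time-by-arm interaction differs from zero, which is taken to show an effect at follow-up (T2/T3). Whether the interaction is tested once on 2 df or separately at each time point is not stated.

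The same section offers Generalized Estimating Equations as a confirmatory model, but only as something the study may do.

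The measures table in Section 4.3.3 schedules "Beliefs (Self-efficacy/Outcome expectations") and PEPPI-5 at T1, T2 and T3. Barriers, HADS, DAS-4, FACT-B and the PROMIS SexFS are collected at T1 and T3 only. T1 and T3 are mainly online, whereas "post-intervention (T2) data will generally be collected primarily in-person in clinic immediately following the clinic visit which was audio recorded".

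Individual contrasts also matter. Section 1.0 expects larger belief gains at the 2-month follow-up. The Secondary Analyses in 13.3.3 list T3-T1 differences, including for communication self-efficacy and outcome expectancies, and add that "T2-T1 differences will also be analyzed for the beliefs measures".

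**The concern.** With one score per patient per assessment, a time-within-patient effect cannot be separated from the residual in a linear model. What remains is a patient intercept and a provider intercept, so every pair of assessments shares one correlation and every assessment one variance. The standard error of each change then comes from a pooled residual, whichever two assessments are compared.

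There are reasons to doubt equal correlations here. T3 comes 2 months after training, T2 differs from T1 and T3 in its usual setting, and training falls between T1 and T2. If T1 and T3 are the least correlated pair, the model understates the standard error of the 2-month contrast, and its confidence interval covers less than 95%. If T1 and T2 are weakly correlated, the T2-T1 contrast suffers in the same way.

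**Working it through.** **Inputs from the documents.** Two-sided 5% error and 64 analysed patients per arm (13.3.4); 1:1 allocation (4.3.3); beliefs at T1, T2 and T3 (4.3.3).

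**Assumptions.** The correlations (r12, r23, r13) are not in the documents. The calculations also assume equal variances, complete data, an identity link and T1 as the reference time.

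**The plan's own figure.** Section 13.3.4 claims to "have 80% power to detect a standard effect of 0.5, with 5% two-sided type-I error" with 64 per arm. The noncentrality is 0.5 x sqrt(64/2) = 2.83. With 126 df the power is 80.1% (80.7% by the normal approximation), so the figure reproduces. It is a two-group comparison of means and says nothing about the repeated-measures contrasts.

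**Error rate of a single contrast.** On complete data the random-intercept model estimates one correlation, r_bar = (r12 + r23 + r13)/3. With common variance s^2, it takes the variance of a change to be 2s^2(1 - r_bar); the true value is 2s^2(1 - r_ij). The ratio of model to true standard error is k = sqrt[(1 - r_bar)/(1 - r_ij)], and the true two-sided error is 2 x Phi(-1.96k). The provider effect cancels in a within-patient change, so the provider intercept gives no protection.

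Example, (0.7, 0.7, 0.5): r_bar = 1.9/3 = 0.633.
- T3-T1: k = sqrt(0.367/0.5) = 0.856. The standard error is 14% too small, the error is 9.3%, and a nominal 95% interval covers 90.7%.
- T2-T1: k = sqrt(0.367/0.3) = 1.106. The standard error is 11% too large and the error is 3.0%.

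**Joint 2-df test.** Under no effect the Wald statistic is a weighted sum of two independent 1-df chi-squares. The weights are the eigenvalues of (CWC')^-1(CSC'), where C forms the two changes from T1, S is the true covariance and W the equal-correlation one. In the example the weights are 0.636 and 1.364, and the chance of exceeding 5.99 is 5.5%.

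| Assumed (r12, r23, r13) | T3-T1 | T2-T1 | Joint 2 df |
|---|---|---|---|
| (0.6, 0.6, 0.6) | 5.0% | 5.0% | 5.0% |
| (0.6, 0.6, 0.55) | 5.9% | 4.5% | 5.0% |
| (0.7, 0.65, 0.6) | 6.7% | 3.4% | 5.1% |
| (0.7, 0.6, 0.5) | 8.0% | 2.4% | 5.3% |
| (0.7, 0.7, 0.5) | 9.3% | 3.0% | 5.5% |
| (0.8, 0.65, 0.55) | 9.2% | 1.1% | 5.7% |
| (0.8, 0.8, 0.64) | 10.0% | 2.7% | 5.7% |
| (0.5, 0.7, 0.5) | 6.8% | 6.8% | 5.4% |
| (0.6, 0.6, 0.7) | 3.0% | 6.1% | 5.1% |

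The last two rows are not decay patterns. They show T1-T2 weaker than T2-T3, and T1-T3 as the strongest pair.

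**Stronger decay.** Suppose correlation falls continuously with calendar time, with an assumed T1-T2 gap of 2-4 weeks followed by 2 months. Then T3-T1 is 9-11%, T2-T1 is 0.1-1.2%, and the joint test is at most 6.8%.

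**Finite-sample check.** In 40,000 simulated trials with 64 per arm, (0.7, 0.6, 0.5) gave 7.7% for T3-T1, 2.4% for T2-T1 and 5.2% jointly. (0.7, 0.7, 0.49) gave 9.3%, 3.1% and 5.5%. Equal correlations of 0.6 gave 4.9-5.0% throughout.

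**Measures at T1 and T3 only.** With two assessments there is one correlation, so r_bar = r13, k = 1 and there is no error.

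**The case against.** The strongest reply is that the stated belief conclusion rests on the time-by-arm interaction over T2/T3, not on T3-T1 alone. A reader might infer that the primary test runs at 7-10%. The documents do not support that: tested jointly, the interaction stays at about 5-6% in most patterns. This part of the reply stands, subject to one gap, since the plan does not say that the test is joint.

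Second, the text never says that the random effects are intercepts only. That is fair. It is the natural reading of the sentence, not an explicit statement. If the covariance is instead taken as unspecified, the remedy is the same.

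Third, every error rate above 5% rests on assumed correlations. This also stands. The timing is uncertain too: the 2-4 weeks in Section 4.1.2 describes how far ahead of the visit patients are contacted, not the T1-T2 gap, which is not stated. The online/clinic difference is only the usual mode, because paper, mail and telephone are allowed.

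Fourth, a sensitivity analysis by Generalized Estimating Equations is foreseen. With robust standard errors it would largely deal with the problem, but it is optional, and robust errors are named only for the Phase II models in Section 13.2.3.

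**Conclusion.** The point holds as a specification gap with a bounded effect. Under the random-intercept reading and assumed decay, the T3-T1 contrast of beliefs or PEPPI-5 has a true error of about 6-10%, or up to about 11% if decay follows the assumed calendar gaps. With equal correlations it is 5%.

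A reader might conclude that T2-T1 is always conservative. It is so only when r12 exceeds the average correlation. With (0.5, 0.7, 0.5) it is as liberal as T3-T1, at 6.8%. Since the direction cannot be known beforehand, no simple adjustment of the planned model will do.

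The primary conclusion is only mildly affected if the interaction is tested jointly (about 5-6%, at most about 7%). The larger error would reach it only through separate tests of the two interaction terms. The estimates of precision and confidence intervals reported for T3-T1 and T2-T1 are affected in either case. Measures taken only at T1 and T3 are not.

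**What to change.** In Section 13.3.3, for linear models of beliefs and PEPPI-5, replace the nested-random-effects sentence with: an unstructured 3x3 within-patient covariance over T1, T2 and T3, a random intercept for provider, and Kenward-Roger degrees of freedom. Add two fallbacks: if the model does not converge, a patient random intercept with patient-clustered robust standard errors; if a non-linear link is used, Generalized Estimating Equations with robust standard errors.

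State also that the time-by-arm interaction is tested jointly on 2 df, and that the T3-T1 and T2-T1 contrasts with their confidence intervals come from the same model. In that edit, make T1 the explicit reference time, since the present wording of the indicators compares T2 with itself.

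The cost is a few sentences and four extra variance parameters (six in place of two) with about 128 patients, a negligible loss of precision. Each contrast is then at about 5% whatever the true correlations are.
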